V2, 23 OCT 2017	
Section 6.4 Blinding and Randomisation
 
Patient unblinding is also contained within the IRS system to allow the unblinding of patients for both Safety and Statistical purposes within the protocol via web or phone (per Sponsor outlined request).
 
Amended to:
 
Patient unblinding is also contained within the IRS system to allow the unblinding of patients for both Safety and Statistical purposes within the protocol via web or phone. If emergency unblinding is required this responsibility lies solely with the investigator, unblinding for other Safety and Statistical purposes will be managed
	
Response to GNA dated 18Oct17.
 
Response to GNA dated 18Oct17.

	
per Sponsor outlined request.
 
Inclusion Criteria 8
 
Section 7.3 Visit 1 (Day 1)
 
Addition:
 
- Additional Requirements 
Subjects will be required to avoid exposure to direct sunlight from Visit 1 (day 1) until the follow-up visit (day 28).
	
V1, 20 SEPT 2017	Initial	N/A

PROTOCOL SYNOPSIS

TITLE: A randomised, double-blind, placebo-controlled, Phase IIa study evaluating the efficacy and tolerability of IRL790 in Parkinson's disease dyskinesia.
PROTOCOL NO: IRL790C003
INVESTIGATOR STUDY SITES: This study will be conducted at approximately 15 study sites located in the United Kingdom.
OBJECTIVES: Primary objective: To evaluate the efficacy of IRL790 in Parkinson's disease dyskinesia. Secondary objectives: To evaluate the effects of IRL790 on core symptoms of Parkinson's disease. To evaluate the pharmacokinetics, safety and tolerability of IRL790 in patients with Parkinson's disease dyskinesia.

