METHODOLOGY: This is a multicentre study where 74 patients with Parkinson's disease exhibiting levodopa induced dyskinesia will be randomised to receive study drug or placebo. Thirty seven patients will be randomised to IRL790 and 37 patients to placebo (1:1 randomisation). Patients will be screened for eligibility according to inclusion/exclusion criteria within four weeks of initiation of study treatment (Screening visit). This is an outpatient study with the patients taking the study drug for four weeks at home. IRL790 will be taken twice daily (b.i.d.) as adjunctive treatment to the patients' regular and stable antiparkinsonian medication. The first two weeks of treatment will allow for per patient titration of study medication to the highest tolerated predefined dose, after which patients will continue on this highest tolerated dose for an additional two weeks. Changes in disease state and dyskinesia will be measured using the Unified Parkinson's Disease Rating Scale (MDS-UPDRS) and Unified Dyskinesia Rating Scale (UDysRS); furthermore, patients will administer two 24-hour diaries on run-in and on the fourth week of dosing to assess daily movements. Pharmacokinetic (PK) samples will be collected for the determination of concentrations of IRL790 and its metabolites IRL902 and IRL872 in plasma. They will be collected before and after IMP administration at two visits. A Follow-up Visit will be performed for all patients five to eight days after last administration of IMP.
NUMBER OF PATIENTS: Approximately 74 patients will be enrolled. Patients who are enrolled but not treated will be classed as Screen Failures and will be replaced. In the event that a patient withdraws from the study for any reason other than an adverse event or other safety concern, or is lost to follow-up within 30 days of treatment, a new patient will

be enrolled to replace the withdrawn patient. The replacement will be managed through a centrally administered study wide randomisation list. The reason for the patient's withdrawal from the study must be recorded.

INCLUSION/EXCLUSION CRITERIA:

Inclusion criteria

1. Male or female ≥ 18 and ≤ 79 years of age.
2. Signed a current Ethics Committee approved informed consent form.
3. Parkinson's disease, per UK Parkinson's Disease Society (UKPDS) Brain Bank Clinical Diagnostic Criteria.
4. Waking day dyskinesia of $>25\%$ determined as a score of ≥ 2 as per Question 4.1 of the MDS-UPDRS.

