6.4. Blinding and randomisation

This is a double-blind study, thus, the study patients and the site personnel who are making the study assessments will be blinded to the study treatments of IRL790 and Placebo (capsules of IRL790 and placebo will be of identical appearance.).

Treatment allocation (1:1 randomisation) will be performed via a web-based IVRS and based on the randomisation list generated by Endpoint Clinical.

Interactive Randomisation System (IRS):

The Interactive Response System (IRS) will manage the randomisation and IMP inventory supply chain. IRS will deliver the IMP at the correct time for both new and existing patients. IRS will also support the dosing schedules and is used to track patient activities in real time throughout study visits. Real-time web reports and alerts platform (email, fax, SMS) give access to compliance feedback for continuous transparency of the study's progress. Patient unblinding is also contained within the IRS system to allow the unblinding of patients for both Safety and Statistical purposes within the protocol via web or phone. If emergency unblinding is required this responsibility lies solely with the investigator, unblinding for other Safety and Statistical purposes will be managed per Sponsor outlined request. Unblinding access can be controlled within the IRS by role type allowing only the appropriate role to unblind the appropriate patient.

Prolactin Results

Confidential Protocol: IRL790C003	Version: 6 Date: 14 Jan 2019	Page 42 of 128
--------------------------------------	---------------------------------	----------------

It is expected that Prolactin levels will be raised in participants randomised to IRL790. It should be noted that this elevation in Prolactin is not expected to be clinically significant (i.e. will not exceed the upper limit of normal) but is potentially detectable when comparing Visit 4 results to screening.

There is no risk to the analysis of endpoints by unblinding as the Visit 4 safety test results (including Prolactin level) will only be available several hours after performing the UDysRS and other rating tests.

No ratings can be performed after safety test results are received.

Rush Filming Protocol

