11.2. Sample Size/Power Calculation

Seventy Four (74) evaluable patients (37 per group) are sufficient to demonstrate an effect size of 0.67 between the active treatment and control (IRL790 vs Placebo) for the UDysRS primary endpoint with 80% power and type 1 error rate 0.05 (two tailed).

As the drop-out rate is unknown at the outset recruitment will continue across the 15 sites until the total evaluable number of patients required is obtained.

The effect size used is derived from the mean difference between the active and control groups (at the end of the treatment period) standardised according to the pooled 'between' group standard deviation. Estimates for these were obtained from published literature (Table 1).

Table 1: Sources For Effect Size

Reference	Mean Difference (A-P) (Diff) (n per group) After X Weeks Treatment	Pooled Standard Deviation	Effect Size ¹¹
Goetz (2013)[15]	31-23 (14) (30 per group) 4wks Actual values	~12	0.58
Pahwa (2017)[16]	16 - 8 (8) (60 per group) 12wks Change from baseline	~12.3 (SE:1.6)	0.65 ¹²
Pahwa (2015)[17]	16.7 - 6.7 (10) (20 per group) 8wks Change from baseline	~13 (SE: 3)	0.77 ¹³

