4 STATISTICAL AND ANALYTICAL PLANS

4.1 Sample Size Justification

Seventy-Four (74) patients (37 per group) are sufficient to demonstrate an effect size of 0.67 between the active treatment and control (IRL790 vs Placebo) for the UDysRS primary endpoint with 80% power and type 1 error rate 0.05 (two tailed).

The effect size used is derived from the mean difference between the active and control groups (at the end of the treatment period) standardised according to the pooled 'between' group standard deviation. Estimates for these were obtained from published literature (Table 1).

Table 1: Sources For Effect Size

Reference	Mean Difference (A-P) (Diff) (n per group) After X Weeks Treatment	Pooled Standard Deviation	Effect Size ¹
Goetz (2013)	31-23 (14) (30 per group) 4wks Actual values	~12	0.58
Pahwa (2017)	16 - 8 (8) (60 per group) 12wks Change from baseline	~12.3 (SE:1.6)	0.65 ²
Pahwa (2015)	16.7 - 6.7 (10) (20 per group) 8wks Change from baseline	~13 (SE: 3)	0.77 ³

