7.5.4 Safety laboratory

All haematology, clinical chemistry and coagulation laboratory tests will be summarised using listings for Actual values and Change from Screening and presented by treatment group and assessment day for each Hospital site separately (due to assays performed locally).

Additionally, the local laboratory normal ranges will be used to classify the results as: High, Normal or Low and categorical summaries presented overall according to treatment group and assessment visit. Pooling across all sites is possible here due to the categorical classification.

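### Numeric laboratory results are planned only by hospital site and pooled only as High/Normal/Low, so within-range shifts such as the expected prolactin rise are not summarised between arms

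*SAP*

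**What the plan says.** SAP 7.5.4 gives haematology, chemistry and coagulation results as listings of actual values and changes from Screening, split by arm and day, "for each Hospital site separately (due to assays performed locally". It then classifies results as High, Normal or Low against local ranges and pools those categories over all sites, with the remark that the classification is what makes pooling possible. Protocol 11.10.6 has the same two parts, except that the by-site numeric display is descriptive statistics rather than listings. SAP section 8 does not record that difference.

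Vital signs and ECG are treated differently: SAP 7.5.2 and 7.5.3 summarise numeric change from Screening by arm, with no split by site.

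Prolactin is one of the locally assayed chemistry tests in Protocol 8.2.1. Protocol 6.4 expects it to rise on IRL790 in a way that is not clinically significant, that is, "will not exceed the upper limit of normal", yet may be seen when Visit 4 is compared with Screening. Protocol 3.2 treats it as a marker of target engagement, and Protocol 11.8 lists it beside the PK variables. SAP 7.4 names only IRL790 and its two metabolites, and SAP section 8 does not declare the omission.

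On numbers, the synopsis states: "Thirty seven patients will be randomised to IRL790 and 37 patients to placebo (1:1 randomisation" and "This study will be conducted at approximately 15 study sites located in the United Kingdom".

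**The concern.** Splitting a 74-patient trial over about 15 sites leaves two or three patients per arm in each numeric display. No reader can judge a moderate average difference between arms from groups of that size. The one pooled display discards everything that happens inside the normal range. A drift in liver enzymes, creatinine, thyroid tests or prolactin that does not carry patients past a limit would have no planned summary by arm.

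Prolactin matters most because the protocol predicts exactly such a movement and uses it as evidence that the drug reaches its target. As planned, the report could leave that prediction without a between-arm summary.

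The reason given, local assays, is sound for raw values. It does not carry over to change within a patient. Protocol 8.2.1 sends Screening, Visit 4 and Follow-up samples to the local hospital's laboratory, so each patient's own Screening value serves as a reference from the same laboratory. The SAP also already relies on local ranges for its categories, so values scaled to those ranges need no new data.

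**Working it through.** **The plan's own figure.** SAP 4.1 states: "Seventy-Four (74) patients (37 per group) are sufficient to demonstrate an effect size of 0.67 between the active treatment and control", with "80% power and type 1 error rate 0.05 (two tailed". By the normal approximation, n per arm = 2 × (1.960 + 0.842)² / 0.67² = 15.70 / 0.449 = 34.97, so 35. The two-sample t-test gives 35.96, so 36, and power at 37 per arm is 0.811. The plan's 37 per arm is therefore adequate. It was sized for the UDysRS and is used here only as a patient count.

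**Patients per display.** 74 / 15 = 4.93 per site and 37 / 15 = 2.47 per arm per site. The site count is approximate; over an assumed range of 12 to 18 sites, 37/12 = 3.1 and 37/18 = 2.1. If allocation is not balanced by site (no site stratification is stated), a site with 5 patients has a 2 × 0.5⁵ = 6.25% chance of an empty arm, or 15 × 0.0625 = 0.9 sites expected if all 15 had 5 patients.

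**Precision of a between-arm difference in mean change.** Half-width of the 95% interval, in SDs of the change = t(0.975, 2n − 2) × √(2/n):

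- n = 2 per arm: 4.303 × 1.000 = 4.3 SD
- n = 3 per arm: 2.776 × 0.816 = 2.3 SD
- n = 37 per arm, pooled: 1.993 × 0.232 = 0.46 SD

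**Does adjusting for site lose this?** Assume 14 sites split 2/3 and one split 2/2 (14 × 5 + 4 = 74). The information is 14 × (2×3/5) + (2×2/4) = 16.8 + 1 = 17.8, the SE is 1/√17.8 = 0.237 SD, and with 58 degrees of freedom the half-width is 0.47 SD. Almost nothing is lost.

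**How much the categories recover.** Take a shift of 0.67 SD purely as an illustration. If values are normal and the upper limit lies at +1.96 SD, the share above it goes from 2.5% to 9.9%, or from about 0.9 to 3.6 of 37 patients. A comparison of those proportions would have about 26% power. A comparison of pooled means would have 81%, and one within a single site 7% to 10% (2 to 3 per arm). The first figure uses the SD of values and the other two the SD of change, so they line up only if those SDs are similar.

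**Prolactin.** If the rise stays below the upper limit, as Protocol 6.4 expects, it adds no patient to the High category. It can show only as movement from Low to Normal.

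**The case against.** The strongest reply is that the plan is less bare than it may look. A reader might infer that laboratory data are never pooled, or that no numeric shift between arms could be seen at all. Neither is supported: the High/Normal/Low tables are pooled by arm, and the listings hold every patient's change from Screening, which someone could pool later. SAP 4.4 and the opening of SAP section 7 also promise summary statistics in general, by treatment and visit. That text can be read as covering laboratory data, but 7.5.4 is the specific rule and gives a reason for not pooling numbers. At best the SAP is in tension with itself. Pooling from listings afterwards would be unplanned.

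A reader might also quote half-widths of 9.0 SD at 2 patients and 2.5 SD at 3. Those come from t(0.975, n − 1)/√n and describe one arm's mean, not a difference between arms. Protocol 11.10 plans no formal safety analyses, so even the between-arm half-widths show only how little a site display can tell.

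Laboratory safety does not rest on these tables alone. Protocol 9.7 records clinically significant out-of-range values as adverse events, and Protocol section 23 gives the DSMB unblinded laboratory data. Safety and tolerability appear as an objective in the synopsis but not in Protocol 2.2 or SAP 3.1.3. These points stand and limit the weight of the concern. They do not supply a by-arm summary of within-range change.

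On prolactin, Protocol 11.8 places it with variables to be summarised numerically. That does not fill the gap: the SAP drops it, and 11.8 frames its displays around the IRL790 group and its doses, not a comparison with placebo.

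**Conclusion.** The point holds in a limited form. Numeric laboratory change is planned only within sites, at about 2.5 patients per arm, and the pooled display is blind to movement inside the normal range. Pooling would bring the half-width for a between-arm difference from about 2.3 to 4.3 SD down to about 0.46 SD. The expected prolactin rise is the clearest loss, made worse by its undeclared absence from SAP 7.4.

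This rests on about 15 sites of similar size, on each patient's samples being assayed in one laboratory by one method throughout, and, for the 26% figure only, on normal values with the upper limit at +1.96 SD. It does not show that a safety signal would go unnoticed, and it is not a fault in the efficacy analysis. It is a cheap improvement to the reporting.

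**What to change.** Keep the site listings and the High/Normal/Low tables. Add to SAP 7.5.4 a descriptive summary, pooled over sites, by arm and visit, of each patient's change from Screening, with the scale fixed by analyte before unblinding:

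- **Positive analytes where high values matter** (for example liver enzymes, creatinine, thyroid tests, prolactin): ratio to the patient's own Screening value, as geometric mean with 95% interval, or multiples of the local upper limit.
- **Analytes that can be zero or where low values matter** (for example basophils, eosinophils, haemoglobin, platelets, neutrophils, albumin): absolute change in common units, or change scaled to the local reference range. Ratios and multiples of the upper limit do not suit these.
- **Coagulation:** Protocol 8.2.1 allows either PT or INR, so summarise the two separately.

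Name prolactin explicitly in 7.5.4. Then either restore it to SAP 7.4, in line with Protocol 11.8, or declare its removal in SAP section 8. Reconcile the SAP's listings with the protocol's descriptive statistics for the by-site display, and record the outcome in section 8.

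The cost is a few more tables from data already collected. Calibration differences between laboratories will remain to some degree, and a note under the table should say so.

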7.5.5 Adverse events

All AEs will be summarised according to TEAE or Baseline Event following classification of the verbatim terms according to the Medical Dictionary for Regulatory Activities (MedDRA) dictionary. The number and percentage of patients for all classified events will be presented according to System organ class (SOC) and Preferred term (PT) by treatment group and overall.

Separate summaries will be presented for all AEs by event frequency of occurrence and also for all AEs according to Seriousness, Severity and Relationship.

If appropriate separate summaries according to IRL790 maximum tolerated dose received may be used to support the findings.

7.6 Discontinuation

Patients who discontinue from IMP treatment will be tabulated. The reason for discontinuation will be given. For discontinuation due to AE, the AEs will be given.

7.7 Interim Analysis

Not applicable.

8 CHANGES FROM THE CSP

Clinician's Global Impression of Change in overall PD symptoms is assessed at Visit 4 (Day 28) only, and there is hence no comparison from baseline (Day 1) to Visit 4 (Day 28) as stated in the Clinical Study Protocol..

Change in total score of MDS-UPDRS part II+III has been included as a secondary endpoint.

Change in total score of MDS-UPDRS part II, and change in total score of UPDRS part III, have been added as exploratory endpoints.

9 STATISTICAL DELIVERABLES

The following documents will be delivered:

- SAP
- Statistical analyses, summary tables and listings

10 SOFTWARE

All statistical analyses will be performed using SAS Version 9.4 (SAS institute, Cary, NC).

CLINICAL TRIAL CONSULTANTS AB

Protocol Number: IRL790C003 CTC Project Code: 190_14_2018

12.1 Generic tables

Table 12.1-1 Generic table for categorical data

					XXXX	XXX
Category of Q	uestion	Assessment	Visit Name	Result		
XXX	YYY		Visit 8 Day 29	2. MUCH IMPROVED	0	1(17%)/6
				3. MINIMALLY IMPROVED	5(22%)/23	1(17%)/6
				4. NO CHANGE	11(48%)/23	4(67%)/6
				5. MINIMAL WORSENING	4(17%)/23	0
				6. MODERATE WORSENING	3(13%)/23	0

Table 12.1-2 Generic table for continuous data measured at one occasion

		XXXXX(N=25)	XXXXXX (N=7)	Total (N=32)
Age (years)	n/nmiss	25/0	7/0	32/0
	Mean (SD)	71.8 (3.89)	72.7 (5.59)	72 (4.23)

Table 12.1-3 Generic table for continuous data measured at several occasions

						XXX	XXX	
Category of Question	Subcategory for Question	Assessment	Result Category	Visit Name				
A	С	С	Measured value	Visit 2 Day 1	Ν	23	6	
					Mean (SD)	5.7 (1.7)	5.8 (2.4)	
					Median (Min, Max)	5.0 (3, 10)	6.5 (3, 9)	
					95% CI	5.0;6.5	3.3;8.4	
				Visit 7 Day 28	Ν	23	6	
					Mean (SD)	5.2 (2.1)	5.0 (3.0)	
					Median (Min, Max)	5.0 (2, 9)	5.0 (2, 9)	
						95% CI	4.3;6.1	1.8;8.2
				Absolute change	Visit 7 Day 28	Ν	23	6
			f	from pre-dose baseline		Mean (SD)	-0.6 (2.0)	-0.8 (1.6)
					Median (Min, Max)	-1.0 (-5, 4)	0.0 (-4, 0)	
					95% CI	-1.4;0.3	-2.5;0.8	
					Within group p-value	0.1835	0.5000	
			Relative change	Visit 7 Day 28	Ν	23	6	
			from pre-dose baseline (%)		Mean (SD)	-5.5 (42.8)	-16.7 (28.0)	
					Median (Min, Max)	-10.0 (-71, 100)	0.0 (-67, 0)	
					95% CI	-24.0;13.0	-46.0;12.7	
					Within group p-value	0.2498	0.5000	

